Exclusion criteria for both: Any major unstable medical/psychiatric illness (e.g., hospitalization within 90 days, suicide risk, etc.); severe clinical depression/anxiety (with PHQ-9 scores >20); chronic pain condition (e.g., fibromyalgia, migraines for healthy controls, etc.) or sensory abnormalities (e.g., neuropathy, Raynaud's, etc.); current regular (weekly or more often) practice of meditation or other mind-body intervention; diagnosis of medication overuse headache or chronic migraine. Migraineurs will be studied if they have been headache-free the day of the study visit. Participants may be currently taking migraine medications, as long as they do not have a diagnosis of medication overuse headache. Volunteers with no pain ratings to frankly noxious stimuli (temperatures > 49°C) or excessive responses to threshold temperatures (~43°C) will be excluded. Pregnant subjects will be excluded from all portions of the study due to possible unknown risks of frankly noxious stimuli. Due to unknown risks and potential harm to the unborn fetus, sexually active women of childbearing potential must use a reliable method of birth control while participating in this study. Reliable methods of birth control are: abstinence (not having sex), oral contraceptives, intrauterine device (IUD), DepoProvera, tubal ligation, or vasectomy of the partner (with confirmed negative sperm counts) in a monogamous relationship (same partner). An acceptable, although less reliable, method involves the careful use of condoms and spermicidal foam or gel and/or a cervical cap or sponge.

Table 1: Migraine Diagnosis*

- | |
|--|
| 
• At least 5 attacks, not attributable to another disorder, with:
• Headache lasting 4-72 hours (untreated or unsuccessfully treated)• Headache with at least 2 of the 4:
• Unilateral location• Pulsating quality• Moderate or severe pain intensity• Aggravation by or causing avoidance of routine physical activity (e.g. walking or climbing stairs)• During headache at least 1 of the 2:
• Nausea and/or vomiting• Photophobia and phonophobia |
|--|

*According to the International Classification of Headache Disorders-II Guidelines

Study Enrollment Procedures

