Sample Size Calculation: Using the marginal benefit formula for repeated measures (Vickers),⁴⁰ and assuming an average within-person correlation between repeated measurements of 0.5, a sample size of 48/group will give us 80% power to detect an effect size as low as $d=0.62$ for the group main effect (Hypotheses 1a and 1b). Thus, if the average VAS rating in the controls is 3 (± 2 SD), we will be able to detect a VAS rating of 4.24 in migraineurs; smaller differences are unlikely to have clinical significance. For hypothesis 1c, 98 participants will also give us 84% power to detect a bivariate correlation of at least 0.4 between pain catastrophizing scores or emotional reactivity scores and pain unpleasantness levels ($r \leq 0.4$ not likely of clinical significance).

Outcomes

Stimulus-response curves will be generated for each subject using the logarithmic equation: $\log(\text{VAS pain ratings}) = \log(t - 35) * \text{coefficient} + \text{intercept}$ where t represents stimulus temperature.¹ The coefficient and intercept generated for heat pain intensity and heat pain unpleasantness will both be used as outcome variables, as well as scores from the PCS and the DERS.

Data Analyses

Statistical Analyses: We will use mixed effects hierarchical regression models with a distribution and link function appropriate to the outcome (e.g., the best fitting distribution as defined by model selection). Repeated measures within each participant (i.e., experimental trials within a session) will be handled using subject-level random effects. We do not expect missing data for this Aim, given the controlled nature of the experimental session and electronic data capture. The specific analyses are outlined for each hypothesis:

Analyses 1a: We will separately regress the individual pain outcomes (pain intensity, pain unpleasantness) on the factorial effects for group (migraine, control), stimulus (43, 45, 47, and 49 C), and repeated experimental block (1, 2, and 3). Absent any higher order two-way (e.g., group x stimulus) or three-way (e.g., group x stimulus x block) interaction involving group, we will interpret a statistically significant group main effect as evidence that the two groups differ in their experimental pain reports.

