Group: A risk to taking part in this study is the likelihood of receiving an intervention (that requires time and energy) that may not be effective in helping to treat migraines. The classes or other study-related procedures may cause some, all, or none of the side effects listed below.

Most Likely

Gentle stretching can cause muscle soreness if muscles have not been exercised in a long time. Sitting for extended periods of time can be uncomfortable. Chairs will be provided for comfort, and participants will be allowed to move as needed to relieve any discomfort.

Less Likely

With any activity, there is always a risk of injury. The instructor will advise the participants to avoid any posture that causes discomfort or pain. The instructor will be attuned to watching for any problems during each session.

Rare

There have been rare case reports of meditation or yoga causing a brief limited episode of psychiatric illness. However, most of these case reports are in individuals with a prior history of unstable psychiatric illness. There are no known reports of this occurring in anyone in an MBSR class. Having a history of unstable psychiatric illness is an exclusion criteria for participating in this project so therefore we have in place an extra precaution to not encounter this risk.

Description of alternative treatments and procedures. The alternative is to not participate in the study or to refer to the personal physician for standard treatment.

STATISTICAL CONSIDERATIONS

General Design Issues

To examine the hypotheses, we will again rely on mixed effects hierarchical regression models with a distribution and link function appropriate to the outcome (e.g., binomial distribution and logit link for daily migraine probability). These models will allow us to fully utilize all of the information (i.e., rather than simply calculating change scores) by conceptualizing each diary entry as nested within a diary phase (baseline 4 weeks prior to randomization, 8 weeks of treatment, and 3 and 6 months of follow-up), within a person (random effects), who is nested within a treatment group. Missing data will be scrutinized and we will utilize sensitivity analyses and/or multiple imputation as required. The models will be conducted as described below:

Hypothesis 2a: MBSR will decrease the primary outcome of migraine frequency compared to an education control group;

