Hypothesis 2b: MBSR will differentially affect the secondary outcome of the affective component (pain unpleasantness) of experimental heat pain compared to the education control group.

Hypothesis 2c: MBSR will improve the secondary outcomes of mindfulness, emotion regulation, pain acceptance, pain catastrophizing, and headache-related disability compared to an education control group.

Hypothesis 3A: High levels of baseline pain catastrophizing and emotional reactivity scores and high baseline levels of pain unpleasantness for experimental pain will predict the primary outcome response (migraine frequency) to MBSR.

Hypothesis 3B: Changes in mindfulness after MBSR will be directly associated with improvements in migraine frequency.

Sample Size and Randomization

Sample Size Calculation: For hypothesis 2a, using effect sizes from our pilot trial,⁵⁸ and by analyzing the data with our mixed effects hierarchical regression models, 44 participants/group (n=88) will provide >90% power with $\alpha=0.05$ to detect a difference of 1.3 migraine days/month over the course of the trial (used PASS design) (Hypothesis 2a). Hypothesis 2b has a similar power function as Part I of this study. For hypothesis 3: since hypothesis 3b is the most difficult to evaluate, this RCT is powered on this hypothesis. This calculation assumes a multivariable model examining linear changes with the four predictors (plus intercept and slope). A sample size of 88 participants will give us 80% power with effects as small as $R^2 \geq 6\%$ in the variance of the slopes; smaller predictors are unlikely to be clinically significant.¹⁰¹

Randomization: Once 4-week migraine logs are reviewed by study staff to ensure eligibility, participants will be randomized 1:1 to either MBSR or the education control group, stratified by migraine frequency (low frequency of 4-9 headaches/month or high frequency of 10-20 headaches/month). Treatment assignments will be generated by a permuted blocks method with randomly varying block size and sealed in numbered, opaque envelopes. [name] will generate the randomization (using the statistical SAS program "PROC PLAN" statement) and deliver the envelopes to the PI. Participants in both groups will continue to track their migraines with their daily REDCap logs for the duration of the trial.

Definition of Populations

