All the secondary outcomes and additional measures will be assessed with these standardized, reliable, well-validated instruments: Five-Facet Mindfulness Questionnaire (mindfulness),^{57,103} DERS (emotion regulation),^{3,104} PCS (pain catastrophizing),^{2,36} Chronic Pain Acceptance Questionnaire (pain acceptance),¹⁰⁵ Herth Hope Index (hope),¹⁰⁶ Life Orientation Test-Revised (optimism),¹⁰⁷ Headache Impact Test-6 (HIT-6) (headache related disability),¹⁰⁸⁻¹¹⁰ Migraine Disability Assessment (MIDAS)-one month (headache related disability),^{111,112} Patient Health Questionnaire-depression module, PHQ-9 (depression),³⁴ Generalized Anxiety Disorder-7, GAD-7 (anxiety),³⁵ Headache Management Self-Efficacy Scale (self-efficacy),¹¹³ Migraine Specific Quality of Life Questionnaire, version 2.1 (MSQv2.1) (quality of life),^{114,115} the Perceived Stress Scale 10, PSS (perceived stress),¹¹⁶ the Brief Resilience Scale, the Resilience Scale for Adults, the Flourishing Scale, the Social Connectedness Scale-Revised (SCS-R), the Pittsburgh Sleep Quality Index, the Allodynia Symptom Checklist (ASC-12), and well-validated NIH Patient Reported Outcomes Measurement Information System (PROMIS) measures of sleep, fatigue, pain interference, satisfaction with participation in social roles, and global health. Changes from baseline to initial follow-up will be primary outcomes; secondary outcomes will include changes from baseline to follow-ups at 3 and 6 months.

Additional Information Collected

Sociodemographic and clinical information will be collected at the screening visit.

Expectations for improvement: Expectations can impact results.^{39,117} At baseline and after the second session, participants will rate their expectations using the Credibility/Expectancy Questionnaire.⁹⁶

Class Attendance and Home Practice: Participants in both groups will track their home activities up to the 6-month follow-up visit via REDCap logs and the instructors will track patient class attendance.

Qualitative Interviews: At the initial follow-up, a 30-minute semi-structured interview will be conducted with participants to further explore areas not captured in our standardized quantitative measures.

Data Analyses

Analysis 2a: The probability that an individual experiences a migraine on any given day will be examined as a function of group (MBSR vs. control) and treatment phase. A statistically significant group x phase interaction will be interpreted as evidence that treatment differentially

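### The random-effects structure of the primary group by phase test (Analysis 2a) is ambiguous, and if it is fitted with a person intercept only its type I error exceeds 5%

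*Combined protocol and SAP*

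**What the plan says.** Part 2, Statistical Considerations, General Design Issues, sets out mixed-effects hierarchical regression, with "binomial distribution and logit link for daily migraine probability" as its example of distribution and link. It describes the data structure as "conceptualizing each diary entry as nested within a diary phase". The phases are "baseline 4 weeks prior to randomization, 8 weeks of treatment, and 3 and 6 months of follow-up", and they lie "within a person (random effects), who is nested within a treatment group". The section presents this as the approach already used in Part 1. There, under Data Analyses, repeated measures "will be handled using subject-level random effects", and experimental block is a fixed factor crossed with group and stimulus.

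Part 2, Data Analyses, Analysis 2a, models the daily probability of migraine on group and phase: "A statistically significant group x phase interaction will be interpreted as evidence that treatment differentially" changed that probability. Polynomial growth curves are allowed if needed.

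For Analysis 2a the plan states no person-by-phase random term, random slope, within-person correlation structure or robust variance. Part 2, Sample Size and Randomization, claims more than 90% power with 44 per group for 1.3 migraine days per month, and gives no SD, base rate or correlation. For Hypothesis 3b the same section refers to variance of slopes between people.

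**The concern.** The test compares changes between phases within a person. A random intercept for the person largely cancels out of such a change, so with that term alone the standard error reflects little more than day-level binomial noise. Two sources of variance are then missing:

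- **Person-to-person variation between phases.** People's migraine frequency may move up or down between phases for reasons unrelated to arm. The plan expects change to differ between people, since Hypotheses 3A and 3B set out to predict it and the power text for 3b relies on slope variance.
- **Runs of migraine days.** Table 1 defines migraine by "Headache lasting 4-72 hours (untreated or unsuccessfully treated", and the endpoint counts calendar days, so one attack can mark several consecutive days. The intercept-only model treats days as independent given the person.

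At stake is the error rate of the primary test: an ineffective program could be declared effective more often than the stated 5%.

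**Working it through.** **1. The plan's own figure.** The power above 90% cannot be reproduced, because its inputs are not given. In a plain two-sided comparison, 90% power needs SD ≤ 1.3 / [(1.96 + 1.2816) × √(2/44)] = 1.88 days. The pilot results in Table 4 imply a larger SD: 1.4/0.32 = 4.4 from the effect size, or 3.3 (t) to 3.6 (z) from the interval of −4.6 to 1.8 with 10 and 9 people. SDs of 3.3 to 4.4 give 46% to 29% power. A repeated-measures model can do better, but the plan does not show what variance it assumed.

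**2. Inputs for the error rate.** From the plan: 28 baseline days, 56 treatment days, 44 per group, alpha 0.05 (taken as two-sided). Assumed, because the documents give none: daily probability p = 0.3, lag-1 day correlation rho, and person-by-phase SD tau in log-odds. At p = 0.3, tau = 0.3 is about 0.3 × 0.21 × 28 = 1.8 days per 28, and tau = 0.2 about 1.2 days.

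**3. Single contrast, treatment versus baseline, approximate formula.** Under independent days a person's log-odds change has variance b = (1/28 + 1/56) / (0.3 × 0.7) = 0.2551. Day correlation multiplies b by (1 + rho)/(1 − rho), and variation between phases adds 2·tau². So

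VIF = [b(1 + rho)/(1 − rho) + 2·tau²] / b, and error = 2[1 − Φ(1.96/√VIF)].

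| rho | tau | VIF | 1.96/√VIF | error |
|---|---|---|---|---|
| 0 | 0 | 1 | 1.960 | 5.0% |
| 0.05 | 0 | 1.105 | 1.864 | 6.2% |
| 0 | 0.2 | 1.314 | 1.710 | 8.7% |
| 0.2 | 0.3 | 2.206 | 1.320 | 18.7% |

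The value rho = 0.05 corresponds to runs averaging 1.5 migraine days at p = 0.3: mean run = 1/[(1 − p)(1 − rho)], so rho = 1 − 1/(0.7 × 1.5) = 0.048. Simulation of this contrast with a person intercept only gave 17% in the last setting.

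**4. Joint test.** Two groups and four phases give (2 − 1)(4 − 1) = 3 df. Two simulations under no effect used 88 people and follow-up phases taken as 90 or 91 days each, with 300 runs (A) and 400 runs (B) per setting. Monte Carlo standard error is about 1 point near 5% and up to nearly 3 points at the higher rates.

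| rho | tau | A: intercept only | B: intercept only | B: plus person-by-phase |
|---|---|---|---|---|
| 0 | 0 | 4-5% | 3.7% | 3.5% |
| 0.2 | 0 | 14% | 15.5% | 7.0% |
| 0 | 0.2 | not run | 14.2% | 4.3% |
| 0.2 | 0.3 | 35% | 39.0% | 6.0% |

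At p = 0.2 the last setting in B gave 35.0% and 5.5%. Over every dependent setting tried in B (rho 0.1 to 0.3, tau 0.2 to 0.5, alone or combined), intercept-only error ran from 8% to 67%, and error with the person-by-phase term from 4% to 7%. In A, person-clustered robust variance brought error to about 4-8%.

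**5. Consequence for power.** Take a single contrast with exactly 90% power when days are independent (ratio of effect to standard error 3.24). With the correct variance the ratio becomes 3.24/√1.314 = 2.83 at tau = 0.2, or 81% power. At rho = 0.2 with tau = 0.3 it becomes 3.24/√2.206 = 2.18, or 59% power. The plan may already have allowed for this variance, but it does not say so.

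**The case against.** The strongest reply is that the plan never commits to a person-intercept-only model. The same sentence puts diary phase inside the person as a level of a hierarchical model, so a random phase-within-person term is a possible reading, and with it error stays at 3.5-7%. Random effects for a person also need not be intercepts: person-specific phase or time effects do not cancel. The slope variance in the Hypothesis 3b power text and the optional growth curves fit that broader reading. This stands, and it is why the defect is ambiguity rather than a stated wrong model. It does not settle the matter, because neither passage is tied to a random term in Analysis 2a, and the Part 1 precedent points to the narrower reading.

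The second reply is that rho and tau have no source in the documents. This also stands. The error rates are conditional illustrations.

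Third, a reader might infer that multi-day attacks are the main problem. The documents do not support that. Seventy-two hours is the upper limit for attacks without effective treatment, Concomitant Interventions lets participants keep their migraine medication, and the endpoint definition anticipates abortive treatment. With runs averaging 1.5 days the effect is about one percentage point on the single contrast. Variation between phases is the larger driver.

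**Conclusion.** The point holds as a defect of specification with a real consequence. The plan leaves the random structure of its primary test open, and the most literal reading gives a test whose error exceeds 5% once there is any dependence beyond the person intercept. The plan's own hypotheses presuppose such dependence.

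Under assumed values the size is about 6-9% for the single contrast with mild dependence. At rho = 0.2 with tau = 0.3 it is about 17-19% for that contrast and 35-39% for the joint test. With a person-by-phase random effect it is 3.5-7%.

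A reader might infer that false positives in this trial will certainly be far above 1 in 20, or that 35-39% estimates its actual error rate. Neither follows: the plan can be read as including the needed term, and the documents give no day correlation or between-phase variance. Clustering by class is a separate matter and is not part of these figures.

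**What to change.** State in General Design Issues and in Analysis 2a that the primary model includes a random phase effect within person in addition to the person effect. Alternatively, state that the group by phase test uses person-clustered robust variance. Either one suffices. If growth curves are used instead of phases, say that the time slopes are random between people.

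Then recheck the stated power above 90% for 1.3 migraine days per month with this variance included, and report the SD, base rate and correlations used.

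The change needs a few sentences in the plan and standard software, and no new data. The cost is a wider interval for the primary effect and possibly a lower stated power.

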No previous studies have used experimental pain to evaluate mechanisms of meditation on migraine. Measures of pain intensity and pain unpleasantness will assess nociceptive processing distinct from clinical pain status, providing a means to determine if clinical pain is differentially susceptible to reduction by MBSR. Further, employing experimental pain methodologies will allow us to distinguish affective from sensory processing, allowing us to test our hypotheses that MBSR reduces the affective more than the sensory experience, and this effect will be greater among patients with a greater affective component to their pain.

We will be able to determine predictors of MBSR response in migraineurs. Identifying simple and inexpensive ways to evaluate response will allow treatments to be targeted to those most likely to benefit.

PRELIMINARY STUDIES

We conducted several epidemiological studies that showed that many adults with neurological conditions, including headaches, use complementary and alternative medicine, despite a lack of evidence.⁸⁴⁻⁸⁹ Further, in adults with migraines/severe headaches in the US, the mind-body therapies of deep breathing, meditation, and yoga are the most commonly used.⁸⁸ However, there have only been a few prior studies with non-standardized meditation and yoga interventions in migraine.⁹⁰⁻⁹² We conducted 2 randomized controlled trials (RCT) of MBSR that demonstrated the safety, feasibility, and efficacy of MBSR in adults with mild cognitive impairment^{93,94} and migraines.⁵⁸ In 19 adults with migraines randomized to either MBSR (n=10) or usual care (n=9), MBSR demonstrated no adverse events, 0% dropout, excellent adherence (daily meditation average: 34±11 minutes; class average: 6/8 sessions), and promising effect sizes across several outcomes, despite being a pilot trial without adequate power (**Table 4**).⁵⁸ Theme analyses from qualitative interviews revealed that MBSR may also decrease emotional reactivity and improve pain cognitive reappraisal processes (e.g., less pain catastrophizing and more pain acceptance). The methods of this pilot trial⁵⁸ will be applied to this research. The results from this study support future studies with larger sample sizes to evaluate mechanisms.

Table 4: Improvements* in MBSR vs. Control Group after MBSR in Adults with Migraines

Measure	Change in MBSR vs. Control, d^f	95% CI^g	Comment
Headaches			Although underpowered, migraines were:

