As done in prior behavioral headache research,⁶⁹ all participants who attend at least ONE class will be included in the intention-to-treat analyses. This is a modified "intent to treat" analysis that ensures exposure to the independent variable and is used and felt to be very important by behavioral scientists.

Outcomes

Our primary outcome will be change in frequency of migraine days, defined as a calendar day (00:00 to 23:59)¹⁰² when the patient reports 4 or more continuous hours of a moderate to severe headache (rating of 6-10 on 0-10 VAS pain intensity scale) and/or they treated a headache with abortive medication. Participants will track their headaches daily with REDCap logs to

demonstrate frequency, severity (both pain intensity and pain unpleasantness, as trained with QST), medications, and associated migraine symptoms (e.g., photophobia, phonophobia, nausea, vomiting). iPod Touch devices with Pendragon software will be available to those without internet access.

Secondary outcomes include changes in migraine severity (measured by pain intensity and unpleasantness on 0-10 VAS scale), migraine duration (hrs), frequency of headache days, headache duration, headache severity (measured by pain intensity and unpleasantness on 0-10 VAS scale), experimental heat pain intensity and unpleasantness (QST measurements), and changes in scores on validated measures of mindfulness, pain acceptance, pain catastrophizing, emotional reactivity, and headache-related disability compared to an education control group; determine factors that predict MBSR response on migraine pain. A headache day is defined as any day when a participant reports the presence of a headache.

We will also characterize participants before/after the intervention using measures of hope, optimism, quality of life, depression, anxiety, perceived stress, self-efficacy, sleep, fatigue, pain interference, satisfaction with participation in social roles, allodynia, and global health.

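### The power of more than 90% stated for Hypothesis 2a is not supported by the pilot frequency effect on which it is said to rest

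*Combined protocol and SAP*

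**What the plan says.** The sample size paragraph of Part 2 (Sample Size and Randomization) addresses Hypothesis 2a. It states that 44 per group (88 in all) gives over 90% power at alpha 0.05 to "detect a difference of 1.3 migraine days/month over the course of the trial". It says this was obtained "using effect sizes from our pilot trial" and "by analyzing the data with our mixed effects hierarchical regression models". It does not name the pilot row, and for this hypothesis it gives no SD, within-person correlation or number of repeated measures.

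The pilot is described under Preliminary Studies: "In 19 adults with migraines randomized to either MBSR (n=10) or usual care (n=9"). Two rows of Table 4 matter here:

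- migraine frequency: -1.4 migraines/month, d=0.32, 95% CI -4.6 to 1.8;
- severity on a 0-10 scale: -1.3 points, d=0.61.

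The Part 2 Outcomes section says "Our primary outcome will be change in frequency of migraine days". The diary phases listed under General Design Issues are "baseline 4 weeks prior to randomization, 8 weeks of treatment, and 3 and 6 months of follow-up". Analysis 2a tests a group-by-phase interaction on the daily probability of migraine.

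**The concern.** The stated source and the stated power do not fit together on their face. A standardised effect of 0.32 is far too small for 44 per group to give 90% power in an ordinary two-group comparison, and the paragraph omits the quantities that would show how a repeated-measures model closes the gap. The target of 1.3 is not the pilot frequency difference. The pilot row counts migraines, whereas the trial outcome counts migraine days.

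The time contrast is also unclear. The sample size paragraph refers to the whole trial. The Outcomes section designates the change from baseline to the first follow-up as primary, although that sentence follows the list of questionnaires and may govern only those.

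This is the power statement for the primary outcome. If the true power is well below the stated one, a null result could be read as excluding a difference of 1.3 days/month more firmly than the design allows.

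**Working it through.** **The plan's own figure.** It cannot be reproduced, because the SD, correlation and number of periods are not given. One can ask what it requires. In a simple comparison, 90% power with 44 per group needs d = (1.960 + 1.282) × √(2/44) = 0.691, that is, an SD of at most 1.3/0.691 = 1.88.

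**SD implied by the pilot frequency row.**
- From d: 1.4/0.32 = 4.375.
- From the CI: half-width (1.8 + 4.6)/2 = 3.2; divided by t(17) = 2.110 this gives an SE of 1.517; divided by √(1/10 + 1/9) it gives an SD of 3.30.

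The two disagree. Table 4 labels its estimates as changes. If the CI reflects change scores, 3.30 already contains some of the gain from baseline, and adjusting it again below favours the plan.

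**Simple comparison, 44 per group, two-sided 0.05, noncentral t.**
- d = 0.32: 32%.
- 1.3 with SD 4.375 (d = 0.297): 28%.
- 1.3 with SD 3.30 (d = 0.394): 45%.

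**Baseline-adjusted repeated measures.** With k post-baseline periods and a common correlation ρ, the variance is multiplied by (1 + (k - 1)ρ)/k - ρ². I take ρ = 0.5 as an assumption; the protocol states that value only for the Part 1 heat-pain ratings. Two 4-week periods correspond to the 8 treatment weeks. Eight correspond roughly to treatment plus six months of follow-up.

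| 4-week periods | Variance factor | Power for 1.3, SD 4.375 | Power for 1.3, SD 3.30 |
|---|---|---|---|
| 1 | 0.750 | 36% | 56% |
| 2 | 0.500 | 50% | 73% |
| 3 | 0.417 | 57% | 81% |
| 8 | 0.3125 | 69% | 90% |

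The normal approximation gives results up to about one point higher, for example 91% in the last cell.

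**Correlation at which 90% is reached.** With SD 4.375: about 0.80 with eight periods pooled, about 0.85 with three. With SD 3.30: about 0.7 with three; eight already suffice at 0.5.

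**Effect of 1.3 versus 1.4.** With SD 4.375, ρ = 0.5 and eight periods, replacing 1.3 by 1.4 raises power from 69% to 76%. The undisclosed SD, correlation and number of periods drive the result.

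**The case against.** The best defence is that a two-sample test is not the planned analysis. The power is attributed to mixed models on daily diary data over the whole trial, and under some inputs such a model does reach 90%. With SD 4.375, three periods at correlation 0.85 give 90.5%. With SD 3.30, three periods at 0.7 give 90.7%. No document sets an upper limit on the correlation. This stands: a reader might infer that 44 per group cannot give 90% power, and the documents do not establish that. They leave the claim undocumented and unsupported by the cited effect size under most readings, not refuted.

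A second tempting inference is that 1.3 was taken from the severity row by mistake. It is the only place in Table 4 with that value, and d=0.61, baseline-adjusted at 0.5 with one follow-up, gives 90.4%. But the target is expressed in migraine days/month, a frequency unit. A detectable difference need not equal the pilot estimate, and the 0.5 is borrowed from Part 1. The match may be coincidence, so a slip cannot be shown.

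It is also true that the protocol says the trial is powered on Hypothesis 3b, so this figure does not set enrolment. That limits the consequence but does not make the statement for the primary outcome correct.

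**Conclusion.** The concern holds in this form: the stated power of more than 90% does not follow from the pilot frequency effect and cannot be reproduced from the documents. For 1.3 per month, the pilot row supports 28% to 45% in a simple comparison. Baseline-adjusted at correlation 0.5, it supports 36% to 56% for one 4-week period, rising to 69% to about 90% with eight pooled. If the primary contrast is baseline to first follow-up (one or two periods), power at that correlation is 36% to 73%.

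These figures assume two-sided testing, equal correlation between all periods, a constant effect across them, and a linear approximation to the daily-probability model. They use a pilot SD in migraines/month as a stand-in for migraine days. The pilot comparator was usual care, whereas here it is an education group matched for time and attention, so the pilot effect may be optimistic for this trial.

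**What to change.** - Name the primary contrast for Hypothesis 2a, reconciling the whole-trial wording in the sample size paragraph with the baseline-to-first-follow-up wording under Outcomes.
- Recompute power for that contrast from the frequency row, stating the SD in migraine-day units, the within-person correlation and the number of diary periods.
- Reconcile 1.3 with the pilot's 1.4, and migraines with migraine days.
- Replace the claim of more than 90% with the resulting power, or with the detectable difference.

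As an illustration only, taking the pilot SD as a stand-in for the migraine-day SD: one baseline-adjusted 4-week period at correlation 0.5 has 80% power for 0.604 × √0.75 × SD, which is about 1.7 (SD 3.30) to 2.3 (SD 4.375) per month.

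The change needs no added patients and no change in conduct. Its cost is a stated figure that is likely to be less favourable.
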